6.1.5. Analysis Visit Windows

Efficacy data will not be windowed and will be analyzed as per the nominal visit present in the database. Efficacy data includes scores on HAM-A, CGI-I, PGI-C, ADN, and IADQ. As described in the Protocol, a ± 2 -day window will be allowed for each visit following Baseline (Visit 2). If a subject attends a visit outside of the window specified in the Protocol, this will be considered an out-of-window visit protocol deviation. Subjects who come in for a visit later than the 2-day window specified in the Protocol, who may have missed days of taking the IP, will be assessed on a case-by-case basis to determine whether they will be included in the analysis. Safety and baseline medical or psychiatric data will not be windowed and will be analyzed as per the nominal visit present in the database. These data include physical examinations, vital signs, clinical laboratory tests, ECGs, adverse events, prior and concomitant medications, and data from the MINI, MADRS, PWC-20, C-SSRS, LSAS, and CGI-S. Unscheduled assessments of safety parameters will be included in listings only.

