	
investigational product (IP) and will be dispensed a 1-week supply of PH94B or placebo. Subjects will then commence 4 weeks of double-blind treatment with the randomized IP 4 times per day.
 
Subjects will return for weekly site visits (Visits 3, 4, and 5), in which the subject will return the IP vials dispensed at the previous visit and receive new vials. Concomitant medications and adverse events (AEs) will be recorded. During these visits, the HAM-A, Patient Global Impression of Change (PGI-C), Clinical Global Impression - Improvement (CGI-I), CGI-S, and C-SSRS will be completed. Vital signs will be collected, and nasal passages will be examined.
 
When the subject returns for Visit 6, besides the assessments completed at Visits 3 through 5, the subjects will complete the MADRS, ADN, and IADQ; and have a physical examination, ECG, laboratory tests (chemistry and blood), urinalysis, urine drug screen, and urine pregnancy test conducted. Any remaining IP vials will be collected. The subject will then come back after a 1-week washout period for the Follow-up visit (Visit 7). During this visit, AEs and concomitant medications since the last visit will be collected and the HAM-A, C-SSRS, and the 20-item Physician Withdrawal Checklist (PWC-20) will be completed.
 
For each visit following Baseline (Visit 2), a \pm 2-day window will be allowed.
 
Safety considerations:
 
Safety and tolerability of PH94B will be assessed and summarized through changes from screening in clinical laboratory values, ECGs, physical examinations, and vital sign assessments following exposure to PH94B, as well as by comparison of AEs reported during treatment with the IP. To date, limited exposure to PH94B (<2 weeks, <4 doses per day) in over 200 subjects has resulted in no serious AEs (SAEs) and no AEs occurring with statistically greater frequency for the PH94B group than for the placebo group. In addition, the PWC-20 will be administered to document any withdrawal effects that may be occurring.

PLANNED NUMBER OF SUBJECTS	Forty adult subjects will be randomized 1:1 to PH94B or placebo.

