	
Interview Guide for the HAM-A (SIGH-A), after 4 weeks of randomized treatment with the study medication
 
4. Population-level summary measure: Difference in mean HAM-A total score between PH94B-treated and placebo-treated subjects after 4 weeks of treatment5. Anticipated intercurrent event: Treatment discontinuation prior to the planned assessment time frame
SAMPLE SIZE DETERMINATION	A sample size of 40 subjects was selected based on information from published studies on treatments for adjustment disorder suggesting that a clinically meaningful effect size could be estimated using a sample size of 40.
STUDY AND TREATMENT DURATION	
The sequence and maximum duration of the study periods will be as follows:
 
1. Screening and washout: [REDACTED]2. Treatment period: From Visit 2 (Baseline) through Visit 6 (End of Treatment)3. Follow-up period: Follow-up visit (Visit 7) conducted approximately 1 week after last treatment 
The maximum study duration for each subject is approximately 10 weeks.
 
The maximum treatment duration for each subject is 4 weeks.

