4.1. Introduction

Data processing, tabulation of descriptive statistics, calculation of inferential statistics, and graphical representations will primarily use Statistical Analysis System Software (SAS) (release 9.4 or higher). If the use of other software is warranted, the final SAP and the statistical methodology report will detail what software was used for what purposes.

Continuous (quantitative) variable summaries will include the number of subjects (n) with non-missing values, mean, SD, median, minimum, and maximum. The minimum and maximum will be reported with the same degree of precision (i.e., the same number of decimal places) as the observed data. Measures of location (mean and median) will be reported to 1 degree of precision more than the observed data and measures of spread (SD) will be reported to 2 degrees of precision more than the observed data.

Categorical (qualitative) variable summaries will include the frequency and percentage of subjects who are in the category or each possible value. The denominator for the percentage calculation will be based upon the total number of subjects in the study population for the treatment groups unless otherwise specified. Percentages will be presented to 1 decimal place. Counts of zero will be presented without percentages.

Unless otherwise indicated, all statistical tests will be conducted at the 0.05 significance level using 2-tailed tests, and p values will be reported. Corresponding 95% confidence intervals (CIs) will be presented for statistical tests. All p values will be displayed in four decimals and rounded using standard scientific notation (e.g., 0.XXXX). If a p value less than 0.0001 occurs it will be shown in tables as < 0.0001 ; similarly, if a p value greater than 0.9999 occurs, it will be shown in tables as > 0.9999 . Confidence intervals will be reported to 1 degree of precision more than the observed data.

This study is considered a Phase 2a exploratory study under an IND application for PH94B targeting AjDA. Statistical tests will be applied and interpreted to determine feasibility and best approaches for potential Phase 2b and Phase 3 studies.

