4.2. Interim Analysis and Data Monitoring

No interim analyses or data monitoring are planned.

5. Analysis Populations

The following analysis populations are planned for this study:

- **All Subjects Population:** All subjects who sign an informed consent, participate in a Visit 1 (Screening), and are entered into the eCRF will be included in the All Subjects

population. The All Subjects population will be used for summaries of subject disposition.

- **Safety Population:** The Safety population includes all subjects who are dispensed IP and reported administering at least 1 dose of IP. The Safety population will be used for safety analyses. For analyses of the Safety population, each subject will be analyzed by the actual treatment received, even if it differs from the subject's randomized treatment assignment.
- **Intent-to-Treat (ITT) Population:** The ITT population includes all subjects who are randomized and have one documented dose of IP at Visit 2 (Baseline). The ITT population will be used for efficacy analyses. For analyses of the ITT population, each subject will be analyzed by their randomized treatment assignment, even if the subject did not receive the assigned treatment or did not follow the protocol until completion.

Assignment of subjects to populations will be confirmed at a blinded data review meeting to be held before the study database is locked. All protocol deviations that occur during the study will be considered for their severity/impact and will be taken into consideration when subjects are assigned to analysis populations.

6. General Issues for Statistical Analysis

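### SAP 6.1.5 lets late attenders be left out of the ITT efficacy analyses case by case, with no criterion, contrary to the SAP's own ITT definition

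*SAP*

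**What the plan says.** SAP 6.1.5 opens with a general rule: "Efficacy data will not be windowed and will be analyzed as per the nominal visit present in the database". It classes a visit outside the protocol's 2-day allowance as a protocol deviation. It then turns to subjects who come later than that, "who may have missed days of taking the IP", and says they "will be assessed on a case-by-case basis to determine whether they will be included in the analysis".

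SAP Section 5 defines ITT as randomized with one documented dose at Visit 2, uses ITT for efficacy, and analyzes each subject in the randomized arm "even if the subject did not receive the assigned treatment or did not follow the protocol until completion". The same section says that protocol deviations "will be taken into consideration when subjects are assigned to analysis populations". Protocol 13.1.1 puts all efficacy analyses on ITT.

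There are safeguards. Populations are confirmed at a blinded review before database lock (SAP Section 5). SAP 7.2 bases the decision on a final deviation listing, before unblinding, with sponsor approval. SAP 7.2 also says that subjects with an important deviation leave a PP population, but Section 5 defines no such population.

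**The concern.** Attending late and missing doses both happen after randomization. The ITT definition says that this kind of departure does not remove a subject, and the first sentence of 6.1.5 says that timing does not remove a score. The later sentence lets a subject be removed for this reason, with no stated threshold. It does not say whether the subject or only the late visit is removed, and no analysis is planned that keeps the excluded subjects. It also refers to visits in general, so a late Visit 3 would qualify.

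What is at stake is the randomized comparison in a small trial: "Forty adult subjects will be randomized 1:1 to PH94B or placebo". If lateness or missed dosing depends on tolerability or response, and differs by arm, the subjects left for analysis are no longer comparable.

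**Working it through.** **Where the exclusion can act.**

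- SAP 13.2, Table 6: all eight efficacy tables are ITT.
- SAP 8.1: the primary ANCOVA is run on ITT.
- SAP 7.2: the PP population is mentioned, but Section 5 does not define it and no table uses it.
- SAP Tables 3 and 4: the intercurrent events are treatment discontinuation and, in Table 3, prohibited medication. Late attendance and missed doses are in neither table, so the estimand gives no ground for removal.
- SAP Section 11: no such change from the protocol's analysis is listed.

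The only efficacy analyses from which a subject could be left out are therefore the ITT ones. There is also an imbalance. A subject who stops drug and attends Early Termination contributes a Visit 6 score, while one who comes 3 days late may not.

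**Does a late visit show missed dosing?** Inputs: two 8 mL vials per weekly visit and 100 µL per spray (SAP 7.4); 200 µL per dose (SAP 7.4), four times a day; 4 priming sprays per new vial, then one per dose (Protocol 9.2).

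- Supply: 2 × 8 = 16 mL. Initial priming: 2 × 4 × 0.1 = 0.8 mL.
- Daily use: 4 × (0.2 + 0.1) = 1.2 mL.
- Duration: (16 − 0.8) / 1.2 = 12.7 days.

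A visit 3 to 5 days late falls on day 10 to 12 after dispensing, which is within supply. Lateness alone does not show that doses were missed.

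**Effect on the primary test.** There is no plan figure to reproduce. Protocol 13.2 is blacked out, and the synopsis gives only a general rationale ("suggesting that a clinically meaningful effect size could be estimated using a sample size of 40"). The planned ANCOVA (change on treatment and baseline) was therefore simulated. From the documents: 20 per arm and two-sided 0.05 ("all statistical tests will be conducted at the 0.05 significance level using 2-tailed tests"). Assumed: residual SD 1, baseline slope 0.3, no true effect, 2 or 4 subjects dropped, and poor responders picked with weight exp(1.5 × outcome). Each row is 10,000 trials, so the Monte Carlo standard error near 0.05 is √(0.05 × 0.95 / 10,000) = 0.002.

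| Dropped | How chosen | Type I error, none dropped | Type I error, after dropping | Mean estimate after dropping (SD units) |
|---|---|---|---|---|
| 2 | at random | 0.052 | 0.052 | −0.001 |
| 2 | poor responders, both arms | 0.048 | 0.050 | 0.005 |
| 2 | poor responders, active arm only | 0.048 | 0.071 | −0.126 |
| 4 | at random | 0.049 | 0.048 | 0.005 |
| 4 | poor responders, both arms | 0.051 | 0.051 | −0.002 |
| 4 | poor responders, active arm only | 0.049 | 0.117 | −0.243 |

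Negative values favor PH94B. At an assumed HAM-A SD of 5 to 9, the active-arm-only shift is 0.6 to 1.1 points with 2 dropped (0.126 × 5 and × 9) and 1.2 to 2.2 points with 4 dropped (0.243 × 5 and × 9).

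With a true effect of 0.8 SD, one rule for both arms is no longer neutral, because the poor responders come mostly from placebo. With 4 dropped, the mean estimate shrinks from −0.805 to −0.705 and the rejection rate falls from 0.687 to 0.577.

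**The case against.** The sentence does not name a population, and ITT membership is fixed in Section 5. SAP 7.2 lists poor adherence to dosing as an important deviation and sends such subjects out of PP. The late-visit sentence, and the deviation clause in Section 5, may be leftover per-protocol wording. That is plausible as history and is a reason to repair 7.2 as well. It does not settle how 6.1.5 operates, because no PP analysis exists to receive the exclusion. Protocol 13.1.4 allows departures from ITT where specified, but 6.1.5 specifies none.

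The review is blinded, precedes lock, and works from a final deviation listing, in a study declared exploratory. This stands as a limit on deliberate selection. It does not prevent bias if lateness itself follows treatment or response.

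Four stronger readings are tempting, and the documents do not support them:

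- *Late subjects will be removed.* The text permits removal; it does not require it. The deviation clause in Section 5 names no removal from ITT.
- *Reviewers will choose by score.* SAP Section 4 calls for blind review of all collected data, so scores may be in view. Nothing says they inform inclusion.
- *One exclusion switches the imputation method.* With two Visit 6 changes already missing, 2/40 = 0.050 gives mean imputation, while 3/40 = 0.075 or 2/39 = 0.0513 gives multiple imputation. This needs those two missing scores, and either a late score counted as missing, which SAP 6.1.4 does not list, or a subject taken out of the ITT denominator, which no passage states.
- *One or two subjects decide the result.* In 400 simulated null trials, removing the most influential one subject, or one or two, changed significance in 11% and 24%. These are upper bounds. Dropping 2 at random changed it in 2.4%.

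**Conclusion.** The conflict in the wording is established. SAP 6.1.5 contradicts its own first sentence, the ITT definition in Section 5, and Protocol 13.1.1, and it can act only on the ITT efficacy analyses, including the primary.

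The numerical consequence is not established. The documents give no expected number of late visits and no sign that lateness would differ by arm. Under the simulation's assumptions, type I error reaches about 0.07 to 0.12 only in a deliberately bad case, where 2 to 4 poor responders are lost from the active arm alone. A reader might infer that the primary test is invalid as planned, and the material does not show that. It shows an unnecessary discretion with no upper limit, which could bias the primary comparison in either direction and is cheap to remove. It should be changed before the SAP is final.

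**What to change.** 1. Delete the case-by-case sentence in SAP 6.1.5.
2. State in SAP Section 5 that late visits and other protocol deviations never remove a subject from the ITT population.
3. State that a late Visit 6 score enters the primary analysis at its nominal visit, except where the existing Table 3 rules, such as the one for prohibited medication, set it to missing.
4. Add one rule-based sensitivity analysis that sets aside only Visit 6 scores obtained later than the 2-day allowance. Keep Early Termination scores in it: a symmetric window would drop them and create a larger post-randomization exclusion. Say in advance how the scores set aside are handled.
5. Either define the PP population with a planned analysis, or delete the reference in SAP 7.2.

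If the sponsor regards a lapse in dosing before a late visit as relevant to the while-on-treatment strategy, it belongs in Table 3 as an intercurrent event with its own rule.

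Cost: SAP wording and one extra table. No change to data collection or conduct.

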Any laboratory value outside the normal range will be flagged for the attention of the Investigator, who must indicate whether the value is of clinical significance. If the result of any laboratory test performed during Screening (Visit 1) or Baseline (Visit 2) is clinically significant, the subject should not be randomized at Visit 2. However, any abnormal result may be repeated to confirm the finding before excluding the subject from potential inclusion in the study. In addition, subjects should be excluded if they have any other abnormal laboratory test at Screening (Visit 1) that, in the Investigator's judgment, is medically significant in that it would impact the safety of the subject, the conduct of the study, or the interpretation of the study results.

Follow-up/unscheduled laboratory tests may be performed on clinically significant abnormalities as indicated by the Investigator. Unscheduled laboratory tests may be repeated at any time at the discretion of the Investigator for appropriate medical care.

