6.1. Statistical Definitions and Algorithms

6.1.1. Baseline

Baseline for each study assessment (where applicable) is defined in Table 2.

Table 2: Baseline Definitions

Parameters	Baseline
Safety parameters including physical examinations and ECGs.	The last non-missing assessment before the first dose of study drug. This assessment will be at Visit 1 (Screening).
Safety parameters including vital signs, clinical laboratory tests, MADRS, and C-SSRS.	The last non-missing assessment before the first dose of study drug at Visit 2 (Baseline).
Efficacy parameters including HAM-A total score, ADNLM total score, and IADQ total score.	The last non-missing assessment before the first dose of study drug at Visit 2 (Baseline).

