6.1.7.9. Columbia-Suicide Severity Rating Scale (C-SSRS)

The C-SSRS is a semi-structured interview that captures the occurrence, severity, and frequency of suicide-related thoughts and behaviors during the assessment period. The interview includes definitions and suggested questions to solicit the type of information needed to determine if a suicide-related thought or behavior has occurred. The C-SSRS has a “baseline” version, which will be completed at Visit 1 (Screening), and a “since last visit” version that will be completed at all subsequent visits.

There are a maximum of 19 items to be completed: 7 that are required, 10 potential additional items if there is a positive response to a required item, and 2 items for suicide/suicide behavior present during the interview. The C-SSRS uses dichotomous scales (i.e., yes or no), Likert scales, and text or narrative are used to further describe the thoughts or behaviors.

Subjects are considered to have had suicidal ideation during a time period (lifetime, last 6 months, since last visit) if they respond “Yes” to any of the 5 suicidal ideation questions listed below for that time period:

- Wish to be dead (Category 1)
- Non-specific active suicidal thoughts (Category 2)
- Active suicidal ideation with any methods (Category 3)
- Active suicidal ideation with some intent to act, without specific plan (Category 4)
- Active suicidal ideation with specific plan and intent (Category 5)

Subjects are considered to have had suicidal behavior during a time period if they respond “Yes” to any of the 5 suicidal behavior questions listed below for that time period:

- Completed suicide
- Actual attempt

- Interrupted attempt
- Aborted attempt
- Preparatory acts or behavior

Subjects are considered to have suicidal ideation or behavior during a time period if they responded “Yes” to any of the suicidal ideation or behavior questions for that time period.

A subject’s maximum suicidal ideation score is the maximum suicidal ideation category to which they responded “Yes”. Subjects are considered to have treatment emergent suicidal ideation if their maximum suicidal ideation score increased from a previous visit to the next visit after treatment with study drug.

Subjects are considered to have treatment emergent suicidal behavior if they did not have suicidal behavior prior to treatment with study drug but did have suicidal behavior at any visit after treatment with study drug.

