9.4. Electrocardiograms

The number and percentage of subjects with normal and abnormal 12-lead ECG findings will be summarized overall and by treatment group at each study visit. Abnormal results will be grouped as clinically significant and not clinically significant.

Descriptive summaries for the observed results and change from baseline will be presented for 12-lead ECG measures of RR interval (msec), PR interval (msec), QRS interval (msec), and heart rate (bpm) for each treatment group and overall subjects at each study visit. If triplicate reads are taken, the mean of the reads will serve as the observed value at the specific visit.

A comparison of QT results will be presented. Summary statistics for baseline values at Visit 1 (Screening) and Visit 6 will be displayed overall and by treatment group for QT interval (msec) and QT interval corrected for heart rate using Fridericia's formula (QTcF) (msec). In addition, the number and percent of subjects in each treatment group who experienced a change >30 msec or a change >60 msec will be presented.

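### Suicidality recorded only at an unscheduled C-SSRS would be left out of the treatment-emergent rows of Table 14.3.6.4

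*SAP*

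**What the plan says.** SAP 6.1.5 sets the general rule for safety data: "Safety and baseline medical or psychiatric data will not be windowed and will be analyzed as per the nominal visit present in the database". It lists the data meant, including laboratory tests, vital signs, ECGs and the C-SSRS, and ends: "Unscheduled assessments of safety parameters will be included in listings only".

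SAP 6.1.7.9 defines the two treatment-emergent suicidality outcomes. Ideation is treatment-emergent if the "maximum suicidal ideation score increased from a previous visit to the next visit after treatment with study drug". Behavior is treatment-emergent in a subject who had none before study drug but "did have suicidal behavior at any visit after treatment with study drug". SAP 9.7 reports both. The shell of Table 14.3.6.4 shows Visits 1 to 7, followed by the treatment-emergent rows. Its first-page footnote says the table counts subjects who had the event one or more times while on treatment.

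Two neighboring rules matter for the scope of the point. SAP Table 2 defines baseline as "The last non-missing assessment before the first dose of study drug", with a visit named in each row. SAP 9.4 reports subjects "who experienced a change >30 msec or a change >60 msec will be presented" for QT and QTcF.

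**The concern.** Extra assessments are usually made because someone is worried, so they are a likely place to find an event. A rule that sends all of them to listings can leave a positive C-SSRS out of the table meant to count treatment-emergent suicidality. Safety and tolerability form the trial's secondary objective, and suicidal ideation is a named safety endpoint. Protocol 7.2 uses the C-SSRS at every visit as a precaution. There is no data safety monitoring board (protocol 12) and no data monitoring (SAP 4.2), so the final tables carry much of the safety conclusion.

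**Working it through.** The plan gives no figure to reproduce. The check sets the rules side by side and then sizes one subject.

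**1. Is there an exception?** SAP 6.1.7.9, 9.4 and 9.7 and the shells of Tables 14.3.6.2.3 and 14.3.6.4 were read against 6.1.5. None admits an unscheduled record. Table 14.3.6.4 has no unscheduled row.

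**2. Post-dose effect (assumed subject).** Ideation scores are 0 at every scheduled visit, with one unscheduled post-dose score of 4.
- Scheduled visits only: no increase from one visit to the next, so treatment-emergent ideation = No.
- All records: 0 to 4 is an increase, so treatment-emergent ideation = Yes.

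The same holds for behavior seen only at an unscheduled visit.

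**3. Pre-dose effect (assumed subject).** Behavior is recorded only at an unscheduled C-SSRS between Visit 1 and the first dose, then again at a post-dose scheduled visit.
- Scheduled visits only: no prior behavior, so it counts as treatment-emergent.
- All records: prior behavior exists, so it does not.

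This case is narrow, because the Visit 2 form may itself record the behavior. It still shows that the rule can overcount as well as undercount.

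**4. Size of one subject.** Forty subjects randomized 1:1 give 40/2 = 20 per arm, assuming all are dosed and so enter the Safety population. One subject is 1/20 = 5%. Exact (Clopper-Pearson) 95% limits:

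| Count | Lower | Upper |
|---|---|---|
| 0/20 | 0 | 1 − 0.025^(1/20) = 16.8% |
| 1/20 | 1 − 0.975^(1/20) = 0.1% | 97.5% point of Beta(2, 19) = 24.9% |

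**5. QT counts.** Take assumed QTcF values of 400 msec at baseline, 410 at Visit 6 and 465 on an unscheduled ECG. Visit 6 gives 410 − 400 = +10 (neither threshold met). The unscheduled ECG gives 465 − 400 = +65 (both met). However, Table 14.3.6.2.3 lays the threshold counts out by scheduled visit, with Visit 6 the only post-dose visit and percentages taken at each visit. It plans no count over all post-dose ECGs, so the listings-only rule removes nothing from such a count.

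**6. Baseline.** Protocol 10.3.2.1.1 allows an abnormal result to be repeated before a subject is excluded, and adds: "Unscheduled laboratory tests may be repeated at any time at the discretion of the Investigator for appropriate medical care". SAP 6.1.7.1 takes the last observation before first dose as baseline, which could be such a repeat. The laboratory row of SAP Table 2 ties baseline to Visit 2, and the shell of Table 14.3.5.1 has separate rows for Visit 2 and Baseline. The texts leave open whether a repeat may supply the baseline value.

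**The case against.** The strongest reply is that little is lost. Treatment-emergent adverse events are defined by onset date, not nominal visit (SAP 6.1.7.1), and protocol 11.2.1 treats clinically relevant observations at a visit as adverse events. The C-SSRS record stays in the listings, which can be read in full for 40 subjects. The next scheduled form asks about the period since the last visit and would pick the event up if that means the last scheduled visit. The protocol foresees unscheduled tests explicitly only for laboratories. And since the shell names Visits 1 to 7, the visits in 6.1.7.9 could be read as scheduled ones.

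Most of this stands, as a limit on how often the gap would matter. It does not make the count right. The footnote speaks of events during treatment without tying them to scheduled visits, and no text says whether an unscheduled contact restarts the recall period.

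Several stronger readings are tempting, but the documents do not support them:

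- *The rule can only hide events.* Step 3 shows it can also create one.
- *The safety signal disappears.* It may be missing from one table; the adverse-event tables and listings remain.
- *The QT counts are wrong.* They are by-visit counts as designed, so a count over all post-dose ECGs would be an added output.
- *Repeat laboratory values are barred from baseline.* The texts need reconciling, but they do not establish a bar. SAP 9.2 plans no worst-value laboratory count that could be understated.
- *The 12-fold suicide rate in protocol 5.1.1 sets the expected event rate here.* That figure describes adjustment disorder in general. The trial excludes significant suicide risk, recent attempts and C-SSRS ideation items 4 or 5 (protocol 8.2.2).

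**Conclusion.** The point holds for the C-SSRS treatment-emergent rows. Applied as written, SAP 6.1.5 leaves out a subject whose only positive post-dose C-SSRS is unscheduled. That is at odds with the wording of 6.1.7.9 and with the table's own footnote. Each affected subject is worth 5 percentage points in an arm of 20, enough to change a row from one event to none. How many subjects would be affected cannot be estimated from the documents, and the error can run in either direction once pre-dose records are considered. The baseline question is a smaller matter of reconciling SAP 6.1.5, 6.1.7.1 and Table 2. This is worth settling before unblinding, so that nobody has to decide afterwards which suicidality records count.

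**What to change.** Replace the last sentence of SAP 6.1.5 with wording such as:

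> *Unscheduled assessments are excluded from by-visit descriptive statistics. All C-SSRS records, scheduled and unscheduled, are used to derive treatment-emergent suicidal ideation and behavior (pre-dose records for prior status, post-dose records through Visit 7 for emergence), and unscheduled pre-dose records are eligible for the baseline derivation in Table 2.*

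Align the visit wording in SAP Table 2 with this. When coding ideation, state which records are compared. Under the visit-to-visit comparison in 6.1.7.9, a lower unscheduled score between two equal scheduled scores would itself produce an increase.

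Optionally, add an any-post-baseline row to Table 14.3.6.2.3 for the >30 and >60 msec counts that includes unscheduled ECGs. This is a small extra output and not the correction of an error.

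The cost is a few sentences in the SAP and minor programming. No new data, visits or changes to subject care are needed.
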